7.2.2 Visits 5 & 6 (Day 2 & 3)

- Visit 5 is only required for subjects not opting overnight stays for Visit 4. Visit 6 is required for all subjects.

Visits 5 and 6 must be completed at exactly 24 and 48 hours from dose received in Visit 4.

- Review of concomitant medications
- AE assessment
- VS assessment
- Blood samples will be drawn for the following analyses:
 - Chemistry (partial panel)

CCI

○ Serum calcifediol, CCI

CCI

7.2.3 Visits 7, 8, 9 (Day 8, 15, 22)

- Review of concomitant medications
- Dosing compliance and dosing diary assessed for subjects assigned to CTAP101 Capsules and paricalcitol capsules plus low-dose cholecalciferol.
- AE assessment
- VS assessment
- Blood samples for the following analyses:
 - Chemistry (partial panel)

CCI

- Subjects instructed to report to the phase 1 unit for Visit 10 after an overnight fast, and to bring along the previously dispensed study drug containers along with any unused study drug.

7.2.4 Visit 10 (Day 29)

- Subjects admitted into the phase 1 unit (for approximately 14 to 26 hours) after an overnight fast unless Subject chooses to stay overnight. Subjects opting to remain in the phase 1 unit

for overnight will have 24 hour read completed. Those who do not opt to stay overnight, advance to Visit 11.

- Dosing compliance and dosing diary assessed for subjects assigned to CTAP101 Capsules and paricalcitol capsules plus low-dose cholecalciferol.
- Subjects will receive standardized meals while housed in the phase 1 unit. These meals will contain 400 mg of elemental calcium and will be administered at approximately 2 (breakfast), 6 (lunch), and 10 (dinner) hours post-dose.
- Review of concomitant medications
- VS assessment
- Pre-dose blood samples will be drawn for the following:
 - Clinical chemistry (full panel) and hematology
CCI [REDACTED]
- Blood samples will be drawn from subjects housed in the phase 1 unit at approximately 6:00 a.m. ($t=$ ~2 hours), and 8:00 a.m. ($t=$ ~0 hours) and precisely (plus or minus 5 minutes, with exact time noted) at $t=$ 2, 4, 6, 12 and 24 hours (for subjects opting overnight stays) post-dose for the following analyses:
 - Clinical chemistry (partial panel)
CCI [REDACTED]
 - Serum calcifediol, **CCI** [REDACTED]
 - Additional blood samples will be drawn from subjects housed in the phase 1 unit at approximately 8:00 a.m. ($t=$ ~0 hours) and precisely (plus or minus 5 minutes, with exact time noted) at $t=$ 12 and 24 hours (for subjects opting overnight stays), post-dose for the following analysis:
CCI [REDACTED]
- AE assessments will be completed at each timed blood draw (n=6)
- Subjects take next dose of study drug with a sufficient quantity of a non-alcoholic beverage to enable swallowing of the capsules immediately after the $t=$ 0 blood draw, with the exact time of dosing noted.
- Subjects will be discharged from the phase 1 unit after the blood draw at 12 hours post-dose.
- Balance of monthly study drug supply dispensed at discharge to subjects assigned to CTAP101 Capsules and paricalcitol capsules plus low-dose cholecalciferol.

7.2.5 Visits 11 & 12 (Days 30 & 31)

- Visit 11 is only required for subjects not opting overnight stays for Visit 10. Visit 12 is required for all subjects.
Visits 11 and 12 must be completed at exactly 24 and 48 hours from dose received in Visit 10.
- Review of concomitant medications
- AE assessment
- VS assessment
- Blood samples will be drawn for the following analyses:
 - Chemistry (partial panel)

CCI

○ Serum calcifediol, CCI

CCI

7.2.6 Visits 13, 14, 15 (Day 36, 43, 50)

- Review of concomitant medications
- Dosing compliance and dosing diary assessed for subjects assigned to CTAP101 Capsules and paricalcitol capsules plus low-dose cholecalciferol.
- AE assessment
- VS assessment
- Blood samples for the following analyses:
 - Chemistry (partial panel)

CCI

- Subjects instructed to report to the phase 1 unit for Visit 16 with the previously dispensed study drug containers along with any unused study drug.

7.3 End of Study (EOS)

7.3.1 Visit 16 (Day 57) Last study visit (or Early Termination)

- Dosing compliance and dosing diary assessed for subjects assigned to CTAP101 Capsules and paricalcitol capsules plus low-dose cholecalciferol.
- Review of concomitant medications
- AE assessment
- PE (including weight, height and BMI)

- VS assessment
- Serum pregnancy test (for females of child bearing potential)
- Blood samples for the following analyses:
 - Chemistry (full panel) plus hematology

CCI

○ CCI calcifediol, CCI

CCI

CCI

8 QUALITY CONTROL AND ASSURANCE

A quality assurance audit may be performed by the sponsor and/or its designee at selected sites to verify that the study is conducted in accordance with the protocol, ICH/GCP (International Council on Harmonisation [ICH] and Good Clinical Practice [GCP]), and applicable SOPs and regulations, to ensure that the safety and welfare of subjects are addressed, and to confirm that problems reported by study monitors are resolved. Verification of study documents and activities (if applicable) will be conducted to confirm accuracy of recorded data and its analysis. Audit observations and findings will be documented and communicated to appropriate study personnel and management. An inspection may be conducted by regulatory authorities. The Investigator must allow direct access to study documents during these inspections and audits.

Monitoring visits will be performed to evaluate study conduct, data integrity, protocol, and GCP compliance. Each Investigator is responsible for the accuracy, completeness, legibility, and timeliness of the data reported. All source documents are to be completed in a neat, legible manner to ensure accurate interpretation of data. Source documents and laboratory reports will be reviewed to ensure that they are accurate and complete.

To ensure the quality of the clinical data across all subjects and sites, a Clinical Data Management review will be performed by the sponsor or designee on subject data entered or integrated into the electronic data capture (EDC) system. During the review, subject data will be checked for consistency, omissions, and any apparent discrepancies. In addition, the data will be reviewed for adherence to the protocol, and ICH/GCP. Moreover, all data from external sources, e.g., central laboratory and PK/CCP processing/analysis will be reconciled with subject eCRF data. To resolve any questions arising from the Data Management review process, data queries and/or data clarification notifications will be generated via the EDC system for completion and resolution.

9 PLANNED STATISTICAL METHODS

9.1 General Considerations

A detailed description of the PK and ~~CCI~~ for each medication will be described. All data collected on eCRFs and from clinical laboratory evaluations will be grouped and listed by population subgroup, subject number, visit, date and time as feasible. Descriptive summaries of quantitative measures will include the number of subjects, mean, standard deviation (SD), median, minimum, and maximum or as appropriate. In descriptive summary tables, if needed, the geometric mean will be calculated as the n^{th} root of the resulting product of the values, and the coefficient of variation (in percent, %CV) will be calculated as $100^* (SD/[\text{arithmetic mean}])$.

Arithmetic means, SDs, medians, and geometric means will be reported with the same number of significant figures as the reported values. Minimum and maximum values will be reported with the same accuracy as the reported source data. The %CV will be rounded to 1 decimal place.

Denominators of percentage of subject calculations will be based on the number of subjects in the subgroup and selected population unless otherwise specified.

In the event there are multiple results at a given visit and/or time point, the following logic will be applied for purposes of summarization by visit or time point: for pre-dose measurements and selection of a BL value, the more recent non-missing result will be selected; for post-dose measurements, the earliest of the results will be selected. If multiple laboratory results are available for the same date and time and the discrepancy could not be resolved, then the arithmetic mean of the results could be used unless specified in the data management plan or data handling conventions finalized before database lock. All subjects entered into the clinical database will be included in subject data listings.

9.2 Determination of Sample Size

No formal sample size estimation has been performed for the study.

9.3 Randomization

Each subject will be assigned a unique 7 digit subject identification number which will be retained throughout the study and that will be unique across all sites. The 7 digit subject identification number (SSSNNNN) will consist of a 3-digit site number (SSS) and a 4-digit subject number (NNNN) at the applicable clinical site. Should a subject be withdrawn from the study, that subject's 7 digit identification number will not be reassigned.

Randomization will be accomplished in blocks of 4 subjects in a 1:1:1:1 ratio with subjects being assigned to treatment with CTAP101 Capsules, IR calcifediol, high-dose cholecalciferol or paricalcitol plus low-dose cholecalciferol. Randomization will occur during Visit 4 provided that each subject is deemed eligible for enrollment based, in part, on laboratory assessments obtained at two preceding visits (Visits 1 and 2). Laboratory assessments obtained at Visit 3 will not be considered in the determination of enrollment eligibility. In the event that the treatment groups become unbalanced for mean baseline body weight as enrollment progresses, the randomization scheme (described immediately above) will be suspended and subjects will be assigned to treatment groups by the following alternative procedure:

Step 1: Calculate the mean body weight for subjects who have been previously entered into the treatment period, in aggregate and by treatment group.

Step 2: Compare the subject's body weight (measured at Visit 1) with the current mean body weight of all subjects who have previously been entered into the treatment period. If the subject's weight is equal to or higher than the current mean body weight of all previously treated subjects, then assign the subject to a treatment group (which still has less than 20 subjects) having the lowest mean body weight. If the subject's weight is lower than the current mean body weight of all previously treated subjects, then assign the subject to a treatment group (which still has less than 20 subjects) having the highest mean body weight.

Step 3 (if needed): If a subject cannot be assigned to a treatment group according to Step 2 (above) and there are fewer than 80 subjects assigned to treatment, then assign the subject to a treatment group (which still has less than 20 subjects) with the most similar mean body weight.

9.4 Analysis Populations

CCI

The safety population will include all subjects who are randomly assigned to treatment and receive at least 1 dose of study drug. CCI

The PK population will include all subjects who are randomly assigned to treatment, receive at least 1 dose of study drug, have no major protocol deviations, have at least 1 PK data point at BL, and sufficient measureable serum calcifediol or paricalcitol concentrations to facilitate the calculation of at least 1 postdose PK parameter using validated methods.

All planned analyses will be specified in an accompanying statistical analysis plan (SAP).

9.5 Demographics and Baseline Characteristics

Demographic and BL characteristics will be summarized for the ITT, Safety, PP and PK populations. BL height, weight, body mass index (BMI), age, sex, race, ethnicity, tobacco and nicotine history, and alcohol history will be tabulated for the safety population. Age (years) will be calculated as (date of ICF - date of birth + 1)/365.

9.6 Subject Disposition and Withdrawal

Subject disposition will be tabulated and descriptively summarized for all randomized subjects by population subgroups separately and combined. Subject disposition will be summarized by presenting the number and percent of subjects randomized, ITT, Safety, PP and PK subjects, subjects who completed investigational study drug administration, subjects who completed the study, and subjects who discontinued prematurely from the study. The primary reason for premature study termination will be detailed together with the number and percent of subjects discontinuing for each reason. The primary reason for premature study termination will be collected from the ET eCRF page.

Medical history will be displayed in a data listing. Date of diagnoses of CKD and SHPT, stage of CKD, underlying diagnosis of the CKD, and previous and concurrent diseases will be collected in the eCRF and documented on the history of CKD page or as medical history. Medical history events will be sorted alphabetically by System Organ Class (SOC). The coding of the data will be performed with MedDRA version 20.0 or higher, using preferred terms.

9.7 Prior and Concomitant Medications

Prior medications are defined as any continuing or new medication used within 12 weeks and discontinued before Visit 1. Concomitant medications are defined as any continuing or new medication taken from Visit 1 or anytime thereafter until the end of the study. World Health Organization Drug Dictionary Enhanced version September 2017, Format C, or later will be used to code concomitant and prior medications. Prior and concomitant medications will be tabulated by population subgroup using frequency counts and percentages for each anatomical/therapeutic/chemical Class Level 2 and 4 and generic drug name. All medications recorded on the eCRF, including start and stop (or ongoing as of) dates, AE number (if applicable), indication, dose, unit, route, and frequency will be listed. For the purpose of inclusion in prior or concomitant medication tables, incomplete medication start and stop dates will be imputed and then categorized into prior or concomitant medication categories.

9.8 Pharmacokinetic Analysis

Parameters to be calculated in the PK population from observed and BL-adjusted serum calcifediol **CC1** include, but may not be limited to the parameters listed in Table 4.

Table 4 Pharmacokinetic Parameters

[figure not shown]
Parameter	Definition
C_{\max}	Maximum serum concentration.
C_{ss}	Steady state concentration
t_{\max}	Time of maximum serum concentration.
AUC_{0-t}	Area under the serum concentration time curve from time zero to the last measurable time point, calculated by linear-log trapezoidal summation.
$AUC_{0-t'}$	Area under the serum concentration time curve from time zero to a fixed time point t' , calculated by linear-log trapezoidal summation.
λ_z	Terminal rate constant (if estimable), determined by linear regression of the terminal points of the log-linear serum concentration-time curve.
$t_{1/2}$	Terminal elimination half-life (if estimable), determined as $\ln(2) / \lambda_z$.

Non-compartmental method or PK modeling method will be used for the estimation.

Graphical presentation of the concentrations will be provided as needed.

As an exploratory analysis, PK parameters for serum calcifediol will be compared between study arms. These analyses could include simple statistical summaries or using an ANOVA model, if feasible.

CCI

9.10 Safety Analysis

All Safety subjects will be included in the safety analysis. Statistical summary analysis of safety data will be descriptive only.

9.10.1 Primary Endpoints Analyses

9.10.1.1 Adverse Events

All AEs will be collected on the eCRF and coded via SOC and preferred term using MedDRA version 20.0 or higher. Additionally, the intensity of all AEs will be coded using CTCAE v. 5.0. AEs with missing onset date will be treated as TEAEs and missing onset date will be imputed as the date of Visit 1, unless the event end date indicates that the event resolved prior to Visit 1, in which case it will be documented in medical history. AEs with partial onset date will be treated as TEAEs unless the partial onset date or end date of the event is complete enough to indicate that the event started or resolved prior to the administration of the investigational study drug, in which case it will be documented in medical history. Detailed information collected for each TEAE will include: AE number, a description of the event, start date, end date or ongoing as of date, outcome, therapy for event, whether the AE is serious, seriousness criteria (life-threatening, death, hospitalization/prolongation of hospitalization, congenital anomaly, persistent or significant disability/incapacity, required intervention to prevent permanent impairment/damage), severity, and relationship to the study drug. The incidence of the AEs will be summarized by population subgroup for all TEAEs, potentially drug-related TEAEs, serious TEAEs, discontinuation due to TEAEs, TEAEs by relationship to study drug (definite, probable, possible, unrelated) and TEAEs by severity (mild, moderate, severe). The number and percentages of subjects with a TEAE will be summarized by SOC and preferred term and presented overall and by population subgroup. TEAEs will be sorted in descending order of total incidence of SOC and preferred term within each SOC. The percentages will be based on the number of Safety subjects in a particular population subgroup. If a subject has more than one TEAE that code to the same preferred term, the subject will be counted only once for that preferred term. Similarly, if a subject has more than one TEAE within a SOC category, the subject will be counted only once in that SOC category. All AEs collected on the eCRF will be included in the listings. An additional listing of all subject deaths will also be provided.

Diagnostic procedures will be collected separately in the eCRF and coded via SOC and preferred term using MedDRA version 20.0 or higher in a manner similar to AEs.

9.10.1.2 *Vital Signs*

Observed VS values will be summarized descriptively at BL and changes from BL will be descriptively summarized by study arms. Summaries will include n (%), mean, SD, median, minimum, and maximum. Vital sign values will be listed.

9.10.1.3 *Physical Examination*

Physical examination dates, whether a PE is performed or not, abnormalities, if any, will be added to the medical history or reported as AEs as appropriate, and summarized by SOC and preferred term using MedDRA version 20.0 or higher.

9.10.2 *Secondary Endpoint Analyses*

Secondary safety endpoints will include incidence of hypercalcemia and drug-related hyperphosphatemia. The number (n, %) of subjects with hypercalcemia (two consecutive visits with serum calcium above 10.3 mg/dL) or hyperphosphatemia (two consecutive visits with serum phosphorus above 5.5 mg/dL) will be calculated.

9.11 *Efficacy Analyses*

9.11.1 *Primary Endpoint Analyses*

As this study is descriptive in nature there is no planned primary endpoint analyses. Descriptive analysis and plots will be created for the ITT and PP populations of serum calcifediol, CCI [REDACTED]

[REDACTED]

[REDACTED]

[REDACTED]

[REDACTED]

[REDACTED]

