7 STUDY ACTIVITIES

7.1 Screening Period

7.1.1 *Visit 1 (Days -70 or -42 to -36)*

- A signed ICF will be obtained from the subject prior to any study-related procedures
- Review of inclusion/exclusion criteria
- Medical history and demographics
- Review of prior and current medications
- PE (including weight, height and BMI)
- VS assessment
- Serum pregnancy test (for females of child bearing potential)
- Serum hepatitis B and C/HIV screen
- Drugs of abuse screen
- eGFR
- Urinary albumin excretion
- Blood samples will be drawn for the following:
 - Clinical chemistry (full panel) and hematology
CCI [REDACTED]
- Dietary questionnaire for calcium intake and counseling, if needed.

If the screening values do not meet study entry criteria after visit 1, subject may receive supportive care per the investigator's discretion and may be retested once. If values do not fall within study entry criteria on retest, the subject will be considered a screen failure and be withdrawn from the study. Only the screening values that did not meet entry criteria at visit 1 are required to be re-drawn and meet entry criteria at the time of the visit 1 retest.

7.1.2 *Visits 2 and 3 (Within Days -7 to -1)*

- Review of inclusion/exclusion criteria
- Review of concomitant medications
- AE assessment
- VS assessment
- Serum pregnancy test (for females of child bearing potential) (Visit 2 only)
- Blood samples will be drawn for the following:
 - Clinical chemistry (full panel) and hematology
CCI [REDACTED]
- Blood samples will be drawn for:
 - CCI [REDACTED] calcifediol, and CCI [REDACTED]
CCI [REDACTED]

CC1

- [REDACTED]
- Subjects will be instructed to report to the phase 1 unit for Visit 4 after an overnight fast.

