7.2 Treatment Period

7.2.1 Visit 4 (Day 1)

Randomization will occur at the start of this visit.

- Subjects admitted into the phase 1 unit (for approximately 14 to 26 hours) after an overnight fast.
- Subjects will receive standardized meals while housed in the phase 1 unit. These meals will contain approximately 400 mg of elemental calcium and will be administered at approximately 2 (breakfast), 6 (lunch), and 10 (dinner) hours post-dose.
- Review of concomitant medications
- VS assessment
- Blood samples will be drawn from subjects housed in the phase 1 unit at approximately 6:00 a.m. ($t=$ ~2 hours), and 8:00 a.m. ($t=$ ~0 hours) and precisely (plus or minus 5 minutes, with exact time noted) at $t=$ 2, 4, 6, 12 and 24 hours (for subjects opting overnight stays), post-dose for the following analyses:
 - Chemistry (partial panel)

CC1

- Serum calcifediol, CC1
- Additional blood samples will be drawn from subjects housed in the phase 1 unit at approximately 8:00 a.m. ($t=$ ~0 hours) and precisely (plus or minus 5 minutes, with exact time noted) at $t=$ 12 and 24 hours (for subjects opting overnight stays) post-dose for the following analysis:

CC1

 - AE assessments will be completed at each timed blood draw (n=6)
 - Subjects take first dose of study drug with a sufficient quantity of a non-alcoholic beverage to enable swallowing of the capsules immediately after the $t=$ 0 blood draw, with the exact time of dosing noted.

CC1

[REDACTED]

- Subjects will be discharged from the phase 1 unit after the blood draw at 12 hours post-dose unless Subject chooses to stay overnight. Subjects opting to remain in the phase 1 unit for overnight will have 24 hour read completed. Those who do not opt to stay overnight, advance to Visit 5.
- Balance of monthly study drug supply dispensed at discharge to subjects assigned to CTAP101 Capsules and paricalcitol capsules plus low-dose cholecalciferol.

[figure not shown]

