### 3 STUDY DESIGN

#### 3.1 Number of Subjects

Approximately 160 subjects will be screened to enroll approximately 80 eligible subjects with approximately 20 subjects per treatment arm. After signing the informed consent form, prior to any study-related activities, each subject will be assigned a unique 7-digit subject identification number (SSSNNNN) which will be retained throughout the study and that will be unique across all sites. The number will consist of a 3-digit site number (SSS), followed by a 4-digit subject number (NNNN) at the applicable clinical site. Should a subject be withdrawn from the study, that subject's number will not be reassigned.

Randomization will be accomplished in blocks of 4 subjects in a 1:1:1:1 ratio, with subjects assigned to treatment with either CTAP101 Capsules, IR calcifediol, high-dose cholecalciferol, or paricalcitol plus low-dose cholecalciferol. Randomization will occur on Day 1 (Visit 4) provided that each subject is deemed eligible for enrollment based, in part, on laboratory assessments obtained at screening (Days -42 to -36, Visit 1). Laboratory assessments obtained at Days -7 to -1 (Visits 2-3) will not be considered in the determination of enrollment eligibility.

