### 5.5 Handling of Missing Data

Missing data will not be imputed with the exception of incomplete medication start and stop dates and missing onset dates for AEs. Data that are excluded from the descriptive or inferential analyses will be included in the data listings. This will include those measurements from excluded subjects or measurements from unscheduled visits/collections. In calculation of the concentration summaries and displays in graphs, if values are below the limit of quantitation (BLQ) predose they will be set to zero and postdose they will be set to 'missing'; however, they will be presented as BLQ in data listings. If all concentrations at a given time point predose are BLQ, the mean will be presented as zero and the SD and CV% will be reported as not applicable.

For the calculation of PK parameters, BLQ values will be treated as follows:

- BLQ values in samples collected before administration or before the first measurable concentration will be set to zero.

- BLQ values that occur after the first measurable concentration will be set to 'missing.'
- BLQ values that occur at the end of the concentration-time profile will be set to 'missing.'

If both values of the predose average (−2 and 0 hour samples) on Day 29 are missing or BLQ, the minimum concentration for the dosing interval will be used for the calculation of AUC and associated PK parameters, as deemed appropriate. For BL-adjusted profiles, the negative values will be retained for calculation of PK parameters.

CCI

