## 9 SAFETY ANALYSIS

### 9.1 Adverse Events

Adverse events will be coded using MedDRA (Version 21.0 or higher). Each verbatim term will be mapped to a SOC and PT. Severity grades for safety parameters will be assigned using the Common Terminology Criteria for Adverse Events (Version 5.0). When changes in the severity of an AE occur more frequently than once a day, the maximum severity for the experience that day will be noted.

Treatment-emergent AEs (TEAE) are events with onset dates and times on or after the administration of the first dose of study drug and within 30 days after the last dose of study drug, or a continuing AE diagnosed before the date of the first dose of study drug, which increases in frequency, severity, or character during the course of the study.

An overall summary of TEAEs will be provided for the safety population summarizing subjects with at least 1: TEAE, related TEAE, grade 3, 4, or 5 TEAE, serious TEAE, related serious TEAE, TEAE leading to study discontinuation, or related TEAE leading to study discontinuation as well as the number of events within each of the previously mentioned categories by treatment.

In addition, summaries of unique TEAEs will be presented for the safety population by SOC, PT, and by treatment and overall, and will include the number and percentage of subjects who experience the unique event for:

1. All TEAEs,
2. All TEAEs by relationship,
3. All TEAEs by severity grade,
4. All TEAEs leading to study discontinuation,
5. All serious TEAEs, if more than 1 serious TEAE is recorded.

Related TEAEs include all those classified by the investigator as possibly related or related. Unrelated TEAEs are those events classified as not related or unlikely related.

For summaries by relationship, the most related event will be selected. For summaries by severity, the most severe grade will be selected.

Multiple events will be counted only once per subject and treatment in each of the previously mentioned summaries by treatment and overall. In the presentation, SOC and PT will be sorted in alphabetical order.

All AEs captured in the database will be presented in by-subject data listings; however, only TEAEs will be summarized.

MedDRA version will be provided in a footnote in both tables and data listings.

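### Adverse events with a missing onset date are classed as treatment-emergent but dated to screening, and the SAP does not say which governs

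*Protocol*

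**What the plan says.** Protocol 9.10.1.1 gives the rule for a fully missing onset: "AEs with missing onset date will be treated as TEAEs and missing onset date will be imputed as the date of Visit 1". One exception follows: "unless the event end date indicates that the event resolved prior to Visit 1, in which case it will be documented in medical history". The next sentence, on partial onset dates, uses a different cut-off. There the event is a TEAE unless its dates show that it began or resolved before study drug was given, and in that case it too goes to medical history.

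On timing, the heading of protocol 7.1.1 begins "Visit 1 (Days -70 or -42 to -36", and SAP 3.1 refers to "laboratory assessments obtained at screening (Days -42 to -36, Visit 1". Dosing starts at Visit 4, Day 1, where protocol 7.2.1 says "Subjects take first dose of study drug with a sufficient quantity of a non-alcoholic beverage".

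On the definition, protocol 6.6.8 counts onset or worsening from the first dose until 30 days after stopping. SAP 9.1 has two limbs. The first is "events with onset dates and times on or after the administration of the first dose of study drug", up to 30 days after the last dose. The second is "a continuing AE diagnosed before the date of the first dose of study drug, which increases in frequency, severity, or character" during the study. SAP 5.5 names "missing onset dates for AEs" as one of the exceptions to its rule of no imputation, but gives neither the date to use nor a default classification. SAP 9.1 lists all adverse events and summarises only TEAEs.

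**The concern.** The sentence in protocol 9.10.1.1 gives an event a label and a date that cannot both hold under either document's definition of a TEAE. The SAP, where the rule should be settled before database lock, says that a date is imputed and then tests on dates, with no override for imputed ones. The only imputation date in the two documents is Visit 1.

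Adverse events are a primary safety endpoint (protocol 2.2.3), and arms are small, so the classification of single events is visible in the tables. The direction of the error depends on which text the programmer follows, and the plan does not say.

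**Working it through.** The documents give no figure to reproduce. The check is on date logic.

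**Inputs.** Visit 1 is at Day -70 or Days -42 to -36 (protocol 7.1.1), or Days -42 to -36 (SAP 3.1). First dose is Day 1. There is no Day 0, and Day -1 is the day before dosing (SAP 5.6). About 20 subjects per arm (SAP 3.1). Daily arms are dosed for 56 days; the monthly arms on Days 1 and 29 (SAP 3.3).

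**Step 1: distance from first dose.** With no Day 0, Day -k lies k days before first dose. Visit 1 is therefore 36 to 70 days before dosing on the protocol's window, and 36 to 42 days on the SAP's.

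**Step 2: the SAP's onset limb.** The test is Day 1 ≤ onset ≤ last dose + 30 days.
- Onset imputed to Day -70, -42 or -36: the lower bound fails each time, so the event is not a TEAE in any arm. Only the worsening limb can bring it back.
- Onset imputed to Day 1: the lower bound holds, and Day 1 is well inside the upper bound (Day 56 + 30 = Day 86 for daily dosing, Day 29 + 30 = Day 59 for monthly dosing). The event is a TEAE, as the protocol intends.

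**Step 3: the two readings side by side, onset fully missing.**

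| Event ended | SAP date test, onset set to Visit 1 | Protocol classification governs | Consistent with the TEAE definition |
|---|---|---|---|
| Before Visit 1 | Not a TEAE | Medical history | Medical history |
| Between Visit 1 and first dose | Not a TEAE | TEAE (wrong) | Adverse event, not a TEAE |
| After first dose, ongoing, or unknown | Not a TEAE unless it worsened (against the stated intent) | TEAE | TEAE by default |

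Each reading goes wrong in exactly one row.

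**Step 4: is the middle row real?** Adverse events are collected once consent is signed (protocol 6.6.3), consent is taken at Visit 1 (7.1.1), and events are assessed at Visits 2 and 3, before dosing (7.1.2). So there is a pre-dose collection period. For the same reason, an event that resolved before Visit 1 would hardly ever qualify as an adverse event, and the exception removes almost nothing.

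**Step 5: outputs affected.** In SAP Appendix A, the flag drives Tables 14.3.1.1 to 14.3.1.5, and 14.3.1.6 and 14.3.1.7 if produced.

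**Step 6: size per subject.** 1/20 = 0.05, or 5 percentage points of an arm's incidence. This applies to overall TEAE incidence only if the subject has no other TEAE, and to a preferred term only if the subject has no other event of that term.

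**The case against.** The best defence is that the protocol settles the classification in plain words: these events are TEAEs. The SAP never says that it imputes to Visit 1, and SAP 1 names the protocol as a related document. To lose an event, a programmer would have to take the date from the protocol's sentence and ignore the classification in the same sentence. Onset date is a required field (protocol 6.6.2 and 6.6.3), omissions are queried (section 8), and the safety analysis is descriptive only (9.10), so no test or decision rule is involved. All of this stands. It makes the loss possible rather than planned, and probably rare. It does not remove the contradiction, and following the protocol's classification still gives the wrong answer for events that ended before first dose.

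Three stronger readings are tempting and should be resisted.
- A reader might infer that the events vanish from every safety table. They do not. Laboratory, shift, vital-sign, exposure, compliance and hypercalcemia/hyperphosphatemia tables do not use the flag, and the events remain in the by-subject listings (with serious events and deaths in Listing 14.3.2.1).
- A reader might infer that on-treatment events are lost and pre-treatment events are counted at once. These need opposite readings; one algorithm cannot do both.
- A reader might think it enough to replace Visit 1 by first dose in the exception. That clause also sends events to medical history, so the swap would move post-consent, pre-dose events there, against protocol 6.6.3. The partial-date sentence already has this defect.

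**Conclusion.** The rule contradicts itself as written, and the SAP does not resolve it. A literal SAP date test with the protocol's imputed date can remove on-treatment events with missing onset from the TEAE tables. The protocol's classification, taken alone, counts some events that were over before any drug was given. The effect is about 5 percentage points per reclassified subject in an arm of about 20, subject to the condition in step 6. The documents do not give the number of events with missing onset; the expectation that it is small is an assumption, based on the data-collection and query procedures. This is a point worth correcting because the remedy is specific and cheap, not because a large distortion is likely.

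**What to change.** In SAP 5.5 and 9.1, state that an adverse event with a fully missing onset is a TEAE unless its end date is before the first dose. In that case it is a non-treatment-emergent adverse event, listed but not summarised. Implement this either by imputing the onset to the first-dose date or by setting the flag independently of any imputed date. Because the SAP's test uses times as well as dates, the first option also needs a stated time (that of the first dose) or a comparison on dates alone.

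Keep the two boundaries separate. Consent at Visit 1 divides medical history from adverse events (protocol 6.6.3); first dose divides TEAE from non-TEAE and does nothing else. Align both the missing-date and the partial-date sentences in protocol 9.10.1.1 with this.

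The cost is a few sentences in the SAP, which SAP 1 allows by amendment or addendum before database lock, and a protocol clarification. No new data are needed. The one thing to watch is that the edit to the exception does not move post-consent events into medical history.
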